8.1. Analysis Software

Statistical analyses will be performed using SAS Software version 9.3 or higher.

8.2. Withdrawals

Subjects who withdraw from the study prematurely will be considered in all data presentations for which they contribute data. Patients who drop out prematurely or receive rescue treatment for any reason prior to week 32 will also be analyzed as patients with clinically important deterioration in the evaluation of the primary endpoint.

8.3. Handling of Missing Data

In general, missing data will not be imputed, with a few exceptions. If a subject is prematurely withdrawn from the study, or misses data required for the evaluation of the primary endpoint, this subject will be analyzed as having a clinically important deterioration. For missing weight measurements the last available body weight will be used for all calculations related to dosing; in individual patient data listings such last observations carried forward (LOCF) will be tagged.

Missing data in other variables will not be replaced by any method of imputation; instead, the frequency of missing values will be presented.

No analyses of the patterns of missing data will be done.

For adverse events the following will be applied:

An Adverse Event (AE) is defined as treatment-emergent, if first onset or worsening is after start of the first infusion of *octanorm* or placebo.

If the start date and time of an AE are partially or completely missing, the AE will be assumed to be treatment-emergent if it cannot be definitely shown that the AE did not occur or worsen during the treatment emergent period (worst case approach). Missing dates and times will not be replaced.

For medications the following will be applied: A medication will be assumed to be concomitant if it cannot be definitely shown that the medication was not administered during the treatment period as defined in section 8.4 below. Missing dates will not be replaced.

8.4. Derived and Computed Variables

The following derived and computed variables have been initially identified as important for the analysis of the primary and secondary target variables. It is expected that additional variables will be required. The SAP will not be amended for additional variables that are not related to the primary target or key secondary target variables. Any additional derived or computed variables will be identified and documented in the SAS programs that create the analysis files. If the SAP is not amended, further derivations related to primary and secondary target variables will be described in the CSR.

- **Age group:** For subgroup analyses related to age we initially plan for the following age groups: 18-39 years (young adults) / 40-65 years (middle-aged) / >65 years (elderly). In case the actual age distribution of the study population results in groups of very different sizes, these defining intervals might be adjusted in a subsequent SAP, but before the blind is broken.
- **Body Mass Index:** $BMI = (\text{Body weight}) / \text{Height}^2$ [Unit: kg/m²]
- The **treatment period** is defined as the period between the first treatment with study drug (*octanorm* or placebo) to the end of the observation period. This will usually be the termination visit (Week 32 or earlier in case a patient is discontinued from the study).
- **Clinically important Deterioration** is defined as
 - 1) MMT-8 worsening ≥ 6 points (scale of 150) OR CDASI worsening ≥ 5 points, AND
 - 2) A Physician's Global Disease Activity VAS worsening ≥ 2 cm.

9. Study Subjects and Demographics

9.1. Disposition of Subjects and Withdrawals

All subjects screened for the study will be accounted for. For screening failures the reasons for not being enrolled in the study will be listed and summarized.

For all subjects enrolled in the study, descriptive summaries of population data will be provided overall and by treatment group; these will include

- The frequency and percent of subjects in each analysis population by country and overall
- Number of subjects enrolled, randomized, treated, and the number of completers
- Study withdrawals by reason of withdrawal

Individual patient assignments to the analysis populations will be listed, including the reasons for any exclusion from an analysis population.

9.2. Protocol Deviations

Protocol deviations will be checked on complete data for all subjects prior to defining the analysis populations. The final decision regarding inclusion/exclusion of subjects from the analysis sets will be made based on data listings and reports during data review meetings before database lock, data release and final analysis, applying the definitions in section 7.

Major and significant protocol deviations will be summarized by type of deviation. Individual subjects with these protocol deviations will be listed.

A dedicated listing will cover the use of forbidden concomitant medication as detailed in the protocol, section 4.2.2.

9.3. Demographics and Other Baseline Characteristics

Descriptive summaries of the demographic and other baseline characteristics will be completed for the populations specified below, overall and by treatment group; these include:

- Demographics (Age, Gender, Race/Ethnicity, Height, Weight, BMI (calculated))
(SAF, FAS, PP)
- Medical History (SAF)

Medical history will be coded with the Medical Dictionary for Regulatory Activities (MedDRA, according to the version specified in the Data Management Plan). Incidences of findings in medical history will be summarized by MedDRA system organ class (SOC) and preferred term (PT)

- Prior and Concomitant Medications (SAF)

Medications will be coded using the WHO Drug Dictionary (according to the version specified in the Data Management Plan). Incidences of prior and concomitant medications will be summarized by ATC level 2 and ATC level 4

- Baseline Physical Examination
- Participation in study GAM10-08 (SAF)

9.4. Measurement of Treatment Compliance

The following parameters will be listed and summarized per subject and/or per infusion cycle:

- Body weight
- Actual dose (total and per kg body weight, based on the latest available weight measurement)
- Total dose administered
- Total number of infusions administered
- Total volume of solution administered
- Number of infusions
- Infusion times
- Use of premedication
- Overall amount of product administered (only included in data listings)

Deviations from the planned treatment schedule will be summarized by counting the number of infusion sessions that deviate from the scheduled intervals by more than the allowed intervals, and by listing all cases with more than two days deviation individually.

Property of Octapharma. Do not copy or distribute without written permission.

10. Efficacy Analysis

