### **2.2 Secondary Objective(s)**

The secondary objectives of this study are:

- to assess other efficacy outcomes at the end of study (Week 32 or Drop-Out Visit)
- to assess the effect of *octanorm* on Quality of Life (QoL) measures;
- to assess the treatment compliance of home treatment with *octanorm*;
- to evaluate the safety and tolerability of *octanorm* in subjects with DM.

Property of Octapharma. Do not copy or distribute without written permission.

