#### **5.4 Dose and Dosing Schedule**

*octanorm 16.5%* is available in vials with different volumes of solution 12 mL (2 grams) or 48 mL (8 grams). Vials of different volume should be combined in order to reach the required volume of amount of IgG.

Subjects are randomly assigned to *octanorm 16.5%* 0.5 g/kg/week or to placebo (0.9% sodium chloride solution).

If a subject is randomized to receive placebo (0.9% sodium chloride solution), the same volume with the same infusion rate as would have been applied in case the subject would have been randomized to 0.5 g/kg *octanorm 16.5%* will be used.

Body weight is to be measured prior to the first IMP administration and reported to the IRT as it is needed for the calculation of the required IMP dose. Body weight is also to be measured at Visit 5 Week 12, and Visit 8 Week 24. These weight measurements are to be reported to the IRT and will be used by IRT for IMP dose adjustment.

*octanorm* or placebo has to be administered subcutaneously every week ( $\pm 2$  days).

A minimum interval of 4 days must be kept in between two consecutive subcutaneous infusion cycles.

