**Table 5: Time Windows Used in This Study**

Time Point	Time stated	Tolerance
Interval between visits	4 weeks	± 4 days
Interval between infusion cycles	1 week	± 2 days
Interval between infusion sessions	Same day or on two consecutive days or with maximum one day in between two sessions	1 – 54 hours
Vital signs	before IMP administration at the site 1 hour after the infusion session	≤ 60 minutes ± 10 minutes
Direct Coombs' test	before IMP administration at the site	≤ 4 hours
Wells probability score for DVT	after IMP administration at the site	≥ 60 minutes
Wells probability score for PE	after IMP administration at the site	≥ 60 minutes

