## 9.8 Analysis of Compliance of Administered Treatment

The following parameters will be listed and summarized per patient and/or per infusion cycle:

- Body weight
- Actual dose (total and per kg body weight, based on the latest available weight measurement)
- Total dose administered
- Total number of infusions administered
- Total volume of solution administered
- Number of infusions
- Infusion times
- Use of premedication
- Overall amount of product administered (only included in data listings).

Deviations from the planned treatment schedule will be summarized by counting the number of infusion cycles that deviate from the scheduled intervals by more than the allowed intervals, and by listing all cases with more than two days deviation individually.

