3.2.2. Secondary Target Variables

For Efficacy and Quality of Life (QoL), secondary endpoints will be based on:

- The modified Cutaneous Dermatomyositis Disease Area and Severity Index (CDASI): Mean change from baseline (Week 0, defined as end of IgIV therapy) to end of the treatment period (Week 32 or earlier drop-out visit)
- Six Myositis core set measures (CSMs) used for calculation of the Total Improvement Score (TIS), i.e. MMT-8, Physician's Global Disease Activity, Patient's Global Disease Activity, Extra-Muscular Disease Activity, Muscle enzymes, and Health Assessment Questionnaire (HAQ): Mean change from baseline to end the treatment period
- SF-36v2 Health Survey: Mean change from baseline to end the treatment period
- TIS: Mean change from baseline to end the treatment period
- Time to clinically important deterioration during the treatment period
- Number and type of deviations from protocol requirements relating to home treatment (dosing, timing)

For Safety, target variables will be:

Throughout the entire Period:

- Occurrence of all adverse events with particular emphasis on thromboembolic events (TEEs) and hemolytic transfusion reactions (HTRs)
- Local injection site reactions
- Vital signs (blood pressure, heart rate, body temperature and respiratory rate)
- Physical examination
- Laboratory parameters (hematology, clinical chemistry, urinalysis)

At Baseline and end of Treatment Period:

- Tests for viral safety
- Pregnancy test, if applicable

Property of Octapharma. Do not copy or distribute without written permission.

4. Study Methods

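### The planned compliance count does not measure the home-treatment endpoint: no home/on-site split, no dosing deviations, and cycles in the protocol but sessions in the SAP

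*SAP*

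**What the plan says.** Protocol 2.2 lists four secondary objectives. One is "to assess the treatment compliance of home treatment with" the study product. The endpoint that serves it is worded alike in Protocol 3.1.2 and SAP 3.2.2: "Number and type of deviations from protocol requirements relating to home treatment (dosing, timing".

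The analysis sits in Protocol 9.8 and SAP 9.4. The SAP introduces a list of exposure variables with "The following parameters will be listed and summarized per subject and/or per infusion cycle". Dose appears there as an amount, for example "Actual dose (total and per kg body weight, based on the latest available weight measurement". Deviations from the treatment schedule are then summarised by "counting the number of infusion sessions that deviate from the scheduled intervals by more than the allowed intervals", with an individual listing of cases more than two days off. The protocol sentence is the same except for the unit: "counting the number of infusion cycles that deviate from the scheduled intervals by more than the allowed intervals".

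Protocol Table 5 sets two separate tolerances. Cycles are one week apart, plus or minus 2 days. For the two sessions of a cycle the rule is "Same day or on two consecutive days or with maximum one day in between two sessions", with a tolerance of 1 to 54 hours. Protocol 5.4 adds: "A minimum interval of 4 days must be kept in between two consecutive subcutaneous infusion cycles".

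**The concern.** The endpoint has three defining features: it concerns home treatment, it covers dosing as well as timing, and it asks for the type of deviation as well as the number. The planned count has none of them. It ignores where the infusion took place, it looks only at intervals, and it names no categories.

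The counting unit also changes between the documents without explanation. If sections 9.8 and 9.4 are programmed as they stand, the report will contain a pooled timing figure whose meaning depends on an unresolved choice of unit. A stated secondary objective will then have no analysis that answers it.

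**Working it through.** The plan states no figure for this endpoint, so there is none to reproduce. The check is a comparison of texts and a count of sessions.

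**1. Endpoint against analysis**

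| Element of the endpoint | Protocol 9.8 / SAP 9.4 |
|---|---|
| Home treatment | Place of infusion not mentioned |
| Timing | Counted, over all infusions |
| Dosing | Amounts summarised; no deviation defined, no threshold, no count |
| Type | No categories |

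**2. How much of the pooled count is on site**

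Inputs: up to 32 cycles of two sessions (Protocol 3.2). Cycles 1-4 are wholly on site, and at least the first session at Visits 4-9 is on site (Protocol 3.3.1). At least the first session at Visit 3 is on site, and the rest of cycles 5-6 may be home or site (Protocol 6.1.3).

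- Full course: 32 × 2 = 64 sessions.
- Minimum on site: 4 × 2 = 8 in cycles 1-4, plus one session at each of the seven Visits 3-9, gives 8 + 7 = 15. 15/64 = 23.4%, leaving 49 at home.
- Maximum under the routine schedule: cycles 1-6 give 6 × 2 = 12; both sessions at the six Visits 4-9 give 6 × 2 = 12; total 24. 24/64 = 37.5%, leaving 40 at home.

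The maximum leaves out home infusions that the investigator moves to the site for medical reasons.

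The share is higher in a patient who stops early, because the wholly on-site cycles come first. For example, after 12 cycles (24 sessions) the minimum on site is 8 + 2 = 10 (the two being Visits 3 and 4), and 10/24 = 41.7%.

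**3. Cycles or sessions**

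A full course offers 32 units under the protocol and 64 under the SAP. The two counts can differ in either direction of detail:

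- A cycle starts late and its second session follows within 54 hours. The protocol counts one deviation. The SAP count is one or two, depending on whether the second session is also treated as late; Table 5 gives no week-to-week interval for second sessions.
- A cycle starts on time but its sessions are 60 hours apart. The SAP counts one deviation (60 > 54). A count of cycle intervals gives none.

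No fixed conversion links the two counts.

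**4. Whether the allowed interval can be programmed**

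Table 5 permits cycle intervals of 7 − 2 = 5 to 7 + 2 = 9 days. Protocol 5.4 requires at least 4 days between cycles. Neither says whether the interval runs from the start or the end of the earlier cycle.

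- Both measured from start to start: 5 days already exceeds 4, so the 4-day rule never binds.
- The 4-day rule measured from the end of the earlier cycle: sessions on Monday and Wednesday, next cycle on Saturday, gives 5 days from start to start (within Table 5) but 3 days from the end (short of 4).

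The same dates are compliant or not according to a reference point that the documents do not give.

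**The case against.** The best defence is that this is under-specification, and other parts of the plan fill some of the gap. Protocol 4.5 names incorrect dose as a relevant deviation and promises a complete list of minor and major deviations. SAP 9.2 summarises major and significant deviations by type. SAP 10.2 promises full presentation of the secondary efficacy endpoints, with a table list to follow. Protocol 9.3 leaves analysis details to the SAP, so a programmer would normally follow SAP 9.4.

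Much of this stands. SAP 9.4 never calls its count the home endpoint, so the pooling is by omission. But the SAP 9.2 summary is study-wide and restricted to the more serious deviations, and SAP 10.2 gives no method specific to this endpoint. A later table list does not by itself define a dosing deviation or choose a unit. SAP 8.4 defines no variable for it and lets further derivations be described in the study report.

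Four stronger readings are tempting, and the documents do not support them:

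- *The SAP count could be up to twice the protocol count.* Table 5 gives no basis for that factor, and the 60-hour example shows that the ratio has no such limit.
- *A second session 50 hours after the first would be listed as more than two days off.* The listing rule concerns deviation from the schedule. A gap of 50 hours lies within the 54 allowed, so it is no deviation.
- *Dosing deviations will appear nowhere.* Protocol 4.5 and SAP 9.2 would show some. What is missing is their number and type in home treatment.
- *Table 5 and Protocol 5.4 contradict each other.* Both can be satisfied together. The Saturday example conflicts only if the two rules are measured from different points. The reference point is undefined; a contradiction is not shown.

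**Conclusion.** The point holds. The endpoint asks for home-treatment deviations in dosing and timing, by number and type; the only compliance deviation count planned is a timing count over all infusions, in a unit that differs between protocol and SAP. Between 23% and about 38% of the sessions in a full course are on site and would be mixed in. These percentages assume all 32 cycles in two sessions each and the routine division between home and site.

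The consequence is confined to a descriptive secondary endpoint and the home-compliance objective. No hypothesis test, sample-size figure or safety analysis depends on it. It is still worth correcting: the rule as written gives an answer to a different question, and the data needed for the right one are already collected.

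**What to change.** In SAP 9.4, tabulate deviations by arm and by place of infusion, with home infusions as the endpoint and on-site infusions alongside. Count three types separately:

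- (a) cycle-interval deviations, against the Table 5 tolerance for cycles;
- (b) within-cycle session-gap deviations, against the Table 5 tolerance for sessions;
- (c) dosing deviations: administered volume differing from the IRT-assigned volume by more than a margin fixed before unblinding, and missed or incomplete sessions.

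Use as denominator the home sessions or cycles actually due while the patient was on treatment. A planned number will not serve, because it is not fixed (40 to 49 home sessions in a full course) and patients with deterioration stop early. State how cycles with one session on site and one at home are classified.

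Use the same units in Protocol 9.8. Before programming, the sponsor should state the reference point for the cycle interval and reconcile Table 5 with the 4-day minimum in Protocol 5.4. Which reading is right is for the sponsor to settle.

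The cost is some SAP wording, an aligned protocol sentence and a few extra tables. Protocol 5.7.2 already has nurses record the date, volume and speed of home infusions and the site document its own, so no new data collection is foreseen.

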10.1. Primary Endpoint

The primary endpoint measure 'clinically important deterioration' is medically defined in section 8.4, and will be assessed throughout the study until the last visit at Week 32. For the analysis of the primary endpoint, a patient will be considered to have a clinically important deterioration

- (i) if the subject fulfills the definition given in section 8.4 at any time during the treatment period
OR
- (ii) if the subject was withdrawn from the study or received rescue treatment for any reason

If a subject is prematurely withdrawn from the study prior to week 32, or misses data required for the evaluation of the primary endpoint, this subject will be analyzed as a treatment failure, i.e. as having a clinically important deterioration. Because of the double-blind design of the study, and because there is no conceivable connection between the randomized treatment arm and events completely unrelated to study procedure (like e.g. relocation to another city or pregnancy), we trust that any such cases will be distributed uniformly between the treatment arms, and thus not distort the statistical evaluation.

However, to verify this assumption, each withdrawal will be assessed individually by an independent team of medical experts, in compliance with an EU Member State request, and the primary efficacy endpoint will also be analyzed on basis of their individual evaluation of treatment stops. This committee will assess for each patient individually whether she/he should be analyzed as failure or non-failure, based on the reason for treatment stop as well as all other relevant data available. The patients affected by this procedure will be listed with a brief statement justifying the individual classification. This analysis will be done for the FAS and the PP population, and any differences to the primary endpoint outcome will be discussed in the report.

The proportions of patients with clinically important deterioration within the *octanorm* and the placebo arm will be compared by means of the Pearson Chi-square Test for Proportion Difference as implemented in the SAS FREQ-procedure, when specifying the /chisq option for a 2x2 table statement. A confidence level of $\alpha=0.05$ will be applied, and the associated 95% confidence limits for the proportion (risk) difference will be presented.

The pair of hypotheses tested is: $H_0: P_O = P_P$ vs. $H_A: P_O \neq P_P$

where P_O and P_P denote the proportions of patients with clinically important deterioration in the *octanorm* and placebo arm respectively.

The primary efficacy outcome will also be presented for the subgroups defined by age, sex, race (if feasible) and geographical region (North America / Europe). There will be no adjustments for covariates.

Individual patient data listings will be provided for the primary efficacy endpoint, including membership to the analysis sets, individual responses and response criteria fulfilled by visit.

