### 3 INVESTIGATIONAL PLAN

#### 3.1 Primary and Secondary Endpoints

##### 3.1.1 Primary Endpoint(s)

- Proportion of patients with clinically important deterioration in the treatment period. A patient with clinically important deterioration is defined as a patient with 1) MMT-8 worsening  $\geq 6$  points (scale of 150) OR CDASI (Total Activity Score) worsening  $\geq 5$  points, AND 2) a Physician's Global Disease Activity VAS worsening  $\geq 2$  cm.

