#### 4.1.1 Inclusion Criteria

Subjects who meet all of the following criteria are eligible for the study:

1. Subjects with diagnosis of definite or probable DM according to the Bohan and Peter criteria.[29, 30]
2. Subjects who have responded to IGIV treatment as assessed by the treating physician and being on a stable dose for at least 3 months on 2g/kg bodyweight (+/- 10%) prior to study enrolment.
3. For subjects being on other medication(s) for the treatment of DM (immunosuppressants, corticosteroids): a) subject was on such medication(s) at the start of IGIV treatment in the first place, and b) received such medication(s) for at least 3 months prior to study enrolment and at a stable dose for at least 4 weeks prior to study enrolment at the maximally allowed conditions as per Table 2 (see section 4.2.1).
4. MMT-8 score  $\geq 144$ , with at least 3 other CSM to be normal or near normal as per the following criteria: Visual Analogue Scale [VAS] of patient global disease activity  $\leq 2$  cm, physician's global disease activity  $\leq 2$  cm, extra-muscular disease activity  $\leq 2$  cm; no muscle enzyme  $>4$  times upper limit of normal due to myositis, Health Assessment Questionnaire [HAQ]  $\leq 0.25$ .
5. Males or females  $\geq 18$  to  $<80$  years of age.
6. Voluntarily given, fully informed written consent obtained from subject before any study-related procedures are conducted.
7. Subject must be capable and willing to understand and comply with the relevant aspects of the study protocol.

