### 9.2 Statistical Test Procedure

To test the null hypothesis  $H_0$  against the alternative hypothesis  $H_A$  a two-sided Pearson Chi-square Test for Proportion Difference will be performed at a significance level of 5% to compare the placebo group against the high dose group.

If a subject is prematurely withdrawn from the study, or misses data required for the evaluation of the primary endpoint, this subject will be analysed as a treatment failure, i.e. as having a clinically important deterioration.

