#### **9.4 General Principles of Statistical Analysis**

In accordance with the design and objectives of this study, the statistical analysis will include the test of the statistical hypothesis of the study and a summary and detailed description of all data collected during the investigation. Descriptive methods and graphs will be used to present study results for each treatment group. Continuous variables will in general be described by number of valid (evaluable) cases, mean, standard deviation, minimum, lower quartile, median, upper quartile and maximum. Categorical variables will be described by number of cases, frequency and percentage. If appropriate, continuous variables may be categorized and additionally treated as ordinal variables.

The level of significance is set at 0.05 (5%) for the study.

If considered relevant, tests for statistical significance besides the test of the study hypothesis will be presented for important parameters, but shall be interpreted in a descriptive-exploratory way only. No adjustment of level of significance for these tests will be performed.

Where appropriate, 95% confidence intervals for means and proportions will be computed.

The statistical analysis will focus on the comparison between subcutaneous immunoglobulin *octanorm* and placebo on basis of the study endpoints assessed in the 32-week treatment period.

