## **9.10 Handling of Missing Data**

For missing data with respect to the primary endpoint evaluation, please refer to Section 9.7.1.

For missing weight measurements the last available body weight will be used for all calculations related to dosing; in individual patient data listings such last observations carried forward (LOCF) will be tagged.

Missing data in other variables caused by subjects who dropped out of the study or for other reasons will not be replaced by any methods of imputation. Instead, frequency of missing values will be presented.

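### Should the primary analysis include an estimate adjusted for baseline CDASI?

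*SAP*

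**What the plan says.** The confirmatory analysis is a two-sided Pearson chi-square test at 5% in the full analysis set, comparing the proportions with clinically important deterioration (protocol 9.2 and 9.7.1, SAP 10.1). SAP 10.1 adds that "the associated 95% confidence limits for the proportion (risk) difference will be presented". Both documents then state: "There will be no adjustments for covariates". In the protocol this directly follows the sentence on how the null hypothesis is tested.

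The other planned looks at this endpoint are the per-protocol analysis, the independent experts' reclassification of withdrawals, and descriptive subgroups. None is adjusted. Further significance tests are allowed by protocol 9.4, but "shall be interpreted in a descriptive-exploratory way only". SAP section 2 allows exploratory analyses that it does not list, provided the study report identifies them.

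SAP 10.2 does plan baseline adjustment elsewhere. The continuous secondary endpoints, which include CDASI and the individual core set measures, are analysed by ANCOVA with the baseline value as covariate.

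**The concern.** Baseline CDASI is a natural candidate covariate. It is measured before the first infusion (protocol 6.1.2), and its worsening is one of the two alternative limbs of the endpoint: "OR CDASI (Total Activity Score) worsening" by at least 5 points (protocol 3.1.1). MMT-8 must be at least 144 of 150 at entry, but CDASI has no entry limit of its own (protocol 4.1.1). Randomization is in blocks without a described stratification factor (protocol 9.12, SAP 4.3), so chance can leave the arms unequal on CDASI.

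Two things would then seem to be at stake. One is some loss of precision. The other is that, if someone asks whether a CDASI imbalance explains the result, the answer could come only from an analysis labelled as unplanned.

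**Working it through.** **1. The plan's own figure.** Inputs from protocol 9.1 and SAP section 6: completer failure 53.33% (placebo) and 18.89% (octanorm), 10% drop-outs counted as failures, two-sided alpha 0.05, power 80%.

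- Placebo: 0.10 + 0.90 × 0.5333 = 0.58. Octanorm: 0.10 + 0.90 × 0.1889 = 0.27. Difference 0.31, mean 0.425.
- n per arm = [1.96 × √(2 × 0.425 × 0.575) + 0.842 × √(0.58 × 0.42 + 0.27 × 0.73)]² / 0.31² = (1.370 + 0.559)² / 0.0961 = 38.7, so 39.
- Power at 39 per arm is 80.3%.

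The sample size therefore belongs to the unadjusted chi-square, the test that is planned.

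**2. Planned precision.** SE = √[(0.2436 + 0.1971)/39] = 0.1063, so the 95% half-width is 1.96 × 10.63 = 20.8 points at the planning rates. Sample proportions underestimate the variance by a factor of about 38/39, so the interval printed in practice is a little shorter: 20.5 points on average in simulation (Wald limits assumed).

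**3. Chance imbalance.** The difference between arms in a standardized baseline value has SD √(2/39) = 0.226. A difference beyond 0.3 SD has probability 2 × [1 − Φ(0.3/0.226)] = 18.5%. A difference of 0.3 SD would move the unadjusted risk difference by 1.4, 2.5, 3.8 or 4.5 points at odds ratios of 1.3, 1.65, 2.2 or 2.7 per SD. That is 0.13 to 0.42 of the SE. This variation is already part of the 10.63-point SE and of the test's 5% error rate: simulated type I error of the chi-square is 5.1 to 5.2%.

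**4. What adjustment would buy.** The documents do not say how strongly, or in which direction, baseline CDASI predicts deterioration, so a range is assumed. Trials were simulated with 39 per arm and one standard normal covariate acting on deterioration in completers; 10% random drop-outs were then scored as failures. The adjusted estimate is a risk difference standardized from a logistic model with treatment and the covariate. Its robust SE is multiplied by √(78/75) and referred to t with 75 df. Without that correction its type I error is 5.8 to 6.0%.

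| Odds ratio per SD (assumed) | 1.0 | 1.3 | 1.65 | 2.2 | 2.7 |
|---|---|---|---|---|---|
| Sampling SE, adjusted/unadjusted | 1.007 | 1.001 | 0.990 | 0.968 | 0.954 |
| Printed half-width, adjusted (points) | 21.2 | 21.1 | 20.8 | 20.4 | 20.0 |
| Change against the planned interval | +0.6 | +0.5 | +0.25 | −0.2 | −0.55 |
| Change against an equally corrected unadjusted interval (21.15) | 0.0 | −0.1 | −0.35 | −0.8 | −1.15 |

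Differences were taken before rounding. Repeated runs put the SE ratio at 2.7 between 0.945 and 0.954. If the odds ratio is applied to the whole composite, drop-outs included, the SE gain at 2.7 is about 7%.

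Against the interval that the plan would print, the change is +0.6/20.5 = +2.9% to −0.55/20.5 = −2.7%.

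**5. Effect on the conclusion.** With the chi-square as sole confirmatory test, the supportive estimate carries no p-value and adds no power. A power change of −0.3 to +3.8 points would arise only if the adjusted test itself were made confirmatory. The adjusted interval and the chi-square would fall on different sides of significance in 1.6% (odds ratio 1.0) to 7.1% (2.7) of trials.

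**The case for a change.** The best case for the concern is about credibility. A prespecified answer to a question on CDASI imbalance carries more weight than a later one. Adjustment would cut the effect of a 0.3 SD imbalance on the estimate to under 0.1 point. The SAP already accepts baseline adjustment for its secondary endpoints and gives no reason for leaving it out here. Compared like for like, with the same correction on both intervals, the adjusted one is never wider on average.

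All of that is true, and such an estimate would be legitimate. It does not show a fault, for four reasons.

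- **The gain rests on an assumption.** Entry requires MMT-8 of at least 144, "with at least 3 other CSM to be normal or near normal as per the following criteria", which may narrow the spread of CDASI indirectly. Nothing in the documents supports an odds ratio of 2.2 or more.
- **The choice of covariate is open.** Worsening of the physician's global VAS is required for every deterioration, whereas CDASI is one of two alternatives. Baseline VAS, MMT-8 or earlier participation in GAM10-08 could be argued for as well.
- **It adds rules.** A patient who "misses data required for the evaluation of the primary endpoint" stays in the analysis as a failure, so the model would need a covariate value for anyone without baseline CDASI. For other variables, missing values "will not be replaced by any methods of imputation" (protocol 9.10), and SAP 8.3 agrees: "Missing data in other variables will not be replaced by any method of imputation". An exception would be needed in both, and changes to protocol 9.7.1 and 9.10 would be amendments under protocol 10.4.
- **The question can still be answered.** Protocol 9.4 and SAP section 2 leave room for an exploratory adjusted result, and SAP 10.2 already gives baseline-adjusted comparisons of CDASI, MMT-8 and physician VAS themselves.

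**Conclusion.** The concern does not hold. The unadjusted chi-square is a valid test under randomization, is consistent between protocol and SAP, and matches the calculation of 39 per arm. Chance imbalance in baseline CDASI is already covered by its error rate and by the planned interval.

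An added supportive estimate would change the printed half-width by +0.6 to −0.55 points on about 20.5, and would leave the confirmatory conclusion and the power as they are. These sizes assume the planning rates, 39 per arm, Wald limits for the planned interval, random drop-out, and an odds ratio of 1.0 to 2.7 per SD acting in completers. The documents give no figure for that odds ratio. A stronger relation would favour adjustment more, but would not make the planned analysis wrong. Experienced statisticians could choose either way, and the plan needs no change on this point.
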